7.2.1. Screening/Screen Failures

The following will be conducted during the Screening Visit:

- 1. Both the subject and the investigator (or designee) will sign the Informed Consent Form (ICF).
- 2. The Investigator (or designee) will complete an assessment to determine that the subject still meets eligibility criteria.
- 3. The Investigator (or designee) will review the subjects' current medication, medical history, and collect demographics.

4. If the subject does not meet all eligible criteria, the subject will be exited from the study.

Screen failures are defined as subjects who consent to participate in the clinical trial but are not randomized into the study intervention or entered in the study. A minimal set of screen failure information is required to ensure transparent reporting of screen failure subjects, to meet the Consolidated Standards of Reporting Trials (CONSORT) publishing requirements and to respond to queries from regulatory authorities. Minimal information includes demography, screen failure details, eligibility criteria, and any serious adverse event (SAE).

This data will be documented on the appropriate case report form.

7.2.2. Enrollment

Subjects will be considered enrolled in the study when they have signed the IRB/EC approved ICF and have met all eligibility criteria.

7.2.3. Randomization/Blinding/Masking

Enrolled subjects will be randomized into control or intervention arms in a 1:1 allocation using block randomization within subjects strata defined by age-group, sex, and risk-group. Subjects will be assigned to control or intervention arms within each colonoscopist based on a predetermined randomization schedule.

Subjects, investigators, study site personnel, and pathologists will not be blinded to treatment assignments. All Verily personnel involved in the statistical analysis of this study will be blinded to treatment assignment. For the interim analysis, unblinded analysis will be performed by an independent statistician, the results of which will be communicated to a select group of Verily personnel not involved in the study management.

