5.1. Overview

This is a prospective, multi-center, randomized controlled study.

5.2. **Study Objectives and Endpoints**

This study will evaluate the effect of the EVA-C System on Adenomas Per Colonoscopy and Positive Percent Agreement for routine colonoscopies. The control arm is colonoscopy with High Definition White Light Endoscopy (HD-WLE) per standard of care. The intervention arm is colonoscopy with HD-WLE per standard of care plus the EVA-C System.

Adenomas Per Colonoscopy (APC) is defined as the average number of histologically confirmed adenomas resected per colonoscopy.

The following findings are considered positive for the definition of APC, ADR, and other adenoma-related secondary endpoints (where specified):

- Adenoma
- Tubular adenoma •
- Tubulovillous
- Villous
- High Grade Dysplasia

The following pathology findings are **not** considered positive for the definition of APC and ADR, and other adenoma-related secondary endpoints (where specified):

- Serrated-class lesions: •
 - Hyperplastic polyps (HPs)
 - Sessile serrated lesions (with or without dysplasia) (SSLs)
 - Traditional serrated adenomas (TSAs)
- Inflammatory, lymphoid aggregate, normal mucosa

Positive Percent Agreement (PPA) is defined as the total number of histologically confirmed Clinically Significant Excised Lesions, divided by the total number of excisions.

For calculating PPA, Clinically Significant Excised Lesions are defined as follows:

- Neoplastic lesions (Adenoma, Tubular adenoma, Tubulovillous, Villous, High Grade • Dysplasia, Intramucosal carcinoma, Adenocarcinoma);
- Serrated-class lesions classified according to the WHO serrated-class lesion classification below;
- Hyperplastic polyps of the proximal colon (caecum, ascending colon, hepatic flexure, • transverse colon)

According to the World Health Organization (WHO), serrated-class lesions are currently classified into three main categories as follows:

- Hyperplastic polyps
- Sessile serrated lesions (with or without dysplasia), and •

• Traditional serrated adenomas

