5.4. Secondary Endpoints

• Adenoma Detection Rate (ADR)

The Adenoma Detection Rate is defined as the number of patients with at least one histologically confirmed adenoma (the pathology findings that count as positive for adenoma are defined in Section 5.2) divided by the total number of patients enrolled per study arm.

- Evaluation of ADR on the ITT population
- Evaluation of the APC, ADR and PPA endpoints on the Per-Protocol (PP) population
- Evaluation of the APC, ADR and PPA endpoints on a modified Intent-to-Treat (mITT) population that includes only patients in the Screening and Surveillance risk groups

- Subgroup analysis of APC, ADR and PPA in groups defined by age group, sex, risk-group, • site, race, ethnicity, colonoscopist, site, and country
- False Alert Rate (FAR) •

A false alert is defined as a bounding box that persists on the screen (approximately 2-3 seconds per the judgment of the colonoscopist) that is then determined by the colonoscopist not to contain a polyp. The false alert rate is calculated as the number of false alerts per procedure conducted in the intervention arm of the study.

Mean Withdrawal and Inspection Time (MWT) •

The withdrawal time is defined as the time measured from the moment the withdrawal phase of the procedure begins (with the scope in the cecum) to the moment the scope is withdrawn from the patient. The mean Inspection time measurement (also called net withdrawal time) will exclude resection time, and other peri-resection activity not deemed to be colonic inspection. Inspection times for both the control arm and intervention arm will be calculated retrospectively upon review of the video recordings.

Polyp Detection Rate (PDR) •

> Polyp detection rate is defined as the proportion of patients with at least one histologically-confirmed polyp detected.

Proximal Adenoma Detection Rate (pADR) •

pADR is defined as the proportion of patients with at least one histologically-confirmed adenoma (the pathology findings that count as positive for adenoma are defined in Section 5.2) detected in proximal colon (caecum, ascending colon, hepatic flexure, transverse colon).

Flat Adenoma Detection Rate (fADR)

fADR is defined as the proportion of patients with at least one histologically-confirmed non-polypoid adenoma (the pathology findings that count as positive for adenoma are defined in Section 5.2) detected;

Serrated Lesions per Colonoscopy (SLPC) •

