- In the right, transverse, and left colon, lesions are to be removed, at the colonoscopist's discretion, and irrespective of the EVA-C System bounding box, per standard of care. Notably, in the left colon, only those lesions that appear adenomatous are to be removed, per standard of care.
- For bounding boxes that persist on the screen for at least 2-3 seconds (per colonoscopist's discretion) but do not contain a polyp, the colonoscopist will verbally confirm a 'false alert' to the study personnel.

Polyp resection and pathology processing:

- Endoscopic images of each polyp will be acquired before polyp removal.
- Study personnel will record the polyp size (≤ 5 mm, 6-9 mm, ≥ 10 mm), location (cecum, ascending, hepatic flexure, transverse, splenic flexure, descending, sigmoid, rectum), and morphology (Pedunculated 0-Ip, Sessile 0-Is, Flat 0-IIa, or Depressed 0-IIc in accordance with Paris classification²), as reported by the colonoscopist.

 Study personnel will record the time-of-day at the moment the colonoscopist says 'snare closed' (or as the snare is closed) and each polyp will be assigned a number or letter in the sequential order in which it is removed (eg. 1, 2, 3,... or A, B, C, ...) per standard of care.

- If the polyp is not able to be retrieved, the study personnel will note 'not retrieved' in the source documentation.
- Each polyp will be placed into an individually labeled specimen jar with only one polyp per specimen jar. If a polyp trap is used on the endoscope, the polyp trap needs to be advanced/rotated for each new resected polyp.
- The specimen jar will be labeled with the sequential number or letter correlating to the order in which the polyp was removed (eg. 1, 2, 3,... or A, B, C,...) per standard practice.
- The pathology report will note each sequential polyp number or letter and location per standard practice.

Pathology processing guidelines:

- Histopathology will be performed per standard of care with the following recommended guidelines. As assessed by pathologists:
 - For polyp sizes of 1 cm and greater:

Recommend allowing at least 24 hours in formalin for fixation prior to sectioning. Serial section (through stalk, if present) into a maximum of 3 mm blocks. For each block, recommend at least 2 sections will be acquired.

• For polyp sizes greater than 6mm and less than 1cm:

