Bisect or serial section (through stalk, if present) into a maximum of 3 mm blocks. For each block, recommend at least two sections will be acquired.

• For polyp sizes between 3mm and 6mm, inclusive:

Recommend at least two slides with 8 ribbon sections per slide. For 'no significant abnormality' findings, at least 3 serial sequential deeper levels will be performed. Exhaust the block on Pathologist's discretion.

• For polyp sizes less than 3mm:

Recommend to ribbon section block entirely ('exhaust the block' – at least 3 slides)

 Histopathology sections shall be stained and imaged as per standard of care.

Review of Adverse Event, Protocol Deviation, and Device Deficiencies will be completed from time of consent to study exit.

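### Section 7.2.3 leaves pathologists unblinded although their reading decides APC, ADR and the histological part of PPA; masking them is a cheap improvement

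*Combined protocol and SAP*

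**What the plan says.** Section 7.2.3 sets the blinding rule: "Subjects, investigators, study site personnel, and pathologists will not be blinded to treatment assignments". The only people it says will be blinded are the sponsor's statistical analysis personnel.

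The endpoints rest on histology:

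- **APC** (Section 5.2) is "the average number of histologically confirmed adenomas resected per colonoscopy".
- **ADR** (Section 5.4) counts "the number of patients with at least one histologically confirmed adenoma".
- **PPA** (Section 5.2) has as its numerator "the total number of histologically confirmed Clinically Significant Excised Lesions", over all excisions. The list of significant lesions includes "Hyperplastic polyps of the proximal colon".

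Section 7.2.5 describes specimen handling and pathology. Polyp size, location and morphology are recorded "as reported by the colonoscopist". On reporting it says: "The pathology report will note each sequential polyp number or letter and location per standard practice". Histopathology follows standard of care with recommended sectioning guidelines that do not differ by arm. For polyps of 3 to 6 mm one step is left open: "Exhaust the block on Pathologist's discretion". No masked read, central read, second reader or adjudication is described, and no reason is given for an open read.

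**The concern.** In an open-label device trial the usual protection for the endpoint is a blinded assessor. Here the assessor of both co-primary endpoints is the pathologist. ADR, which under Section 13 also feeds the decision on sample size, depends on the same reading. The colonoscopist cannot be blinded to a system that is switched on or off. The pathologist, who reads numbered specimens, can be.

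If a reader knows the arm, borderline tissue could be called differently or worked up further in one arm. A shift favouring the device would raise the chance of a false APC success; a shift the other way would cost power. Even with no shift at all, the rule as written prevents the sponsor from describing the histology as blinded, which leaves a positive result open to criticism.

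**Working it through.** **1. Does the reading decide the endpoints?** Set side by side, Sections 5.2 and 5.4 make histological confirmation necessary for APC, ADR and the PPA numerator. Location is less clear. The bullet on proximal hyperplastic polyps implies that distal ones do not count. The bullet before it, however, admits serrated-class lesions under a WHO list that contains hyperplastic polyps without regard to site. Recorded location therefore enters PPA only if the proximal bullet is meant as a limit.

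**2. How much of the work-up is discretionary?** For 3 to 6 mm polyps, deeper levels follow a fixed trigger (a finding of no significant abnormality) in both arms. Only exhaustion of the block is expressly left to the pathologist.

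**3. The plan's own figure.** Inputs from Section 13: 600 per arm, 15% data loss, ADR 35% versus 45%, one-sided 0.025.

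- n = 600 × 0.85 = 510 per arm.
- SE under the null = √(2 × 0.40 × 0.60/510) = 0.0307. SE under the alternative = √((0.35 × 0.65 + 0.45 × 0.55)/510) = 0.0305.
- Power = Φ((0.10 − 1.96 × 0.0307)/0.0305) = 90.4%. The plan states 90%, so the base is reproduced.
- The stated APC power cannot be reproduced because no mean or SD is given, nor the PPA power because no lesion count is given. Masking changes neither the sample size nor the stated power.

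**4. Illustration for APC.** Assume no true effect and L net extra adenoma readings among 510 device-arm patients. Bias = L/510, and the one-sided error = 1 − Φ(1.96 − bias/SE).

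- Poisson, with P(0) = 0.65: mean = −ln(0.65) = 0.431; SE = √(2 × 0.431/510) = 0.0411.
- Negative binomial, variance/mean k = 3 (assumed), same P(0): mean = 0.431 × (k − 1)/ln k = 0.431 × 2/1.099 = 0.784; SE = √(2 × 0.784 × 3/510) = 0.0961.

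| Net extra readings | APC bias | Error, Poisson | Error, negative binomial |
|---|---|---|---|
| 0 | 0 | 2.5% | 2.5% |
| 5 | 0.0098 | 4.3% | 3.2% |
| 10 | 0.0196 | 6.9% | 4.0% |

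- Lesions needed for 5% error: (1.960 − 1.645) × SE × 510 = 6.6 (Poisson) or 15.4 (negative binomial).
- Five readings in the opposite direction: 1 − Φ(1.96 + 0.239) = 1.4%, or 1 − Φ(1.96 + 0.102) = 2.0%.
- Scale: 5 lesions are 5/(0.431 × 510) = 2.3% of the control adenomas expected under the Poisson model. The Poisson APC difference implied by ADR 35% versus 45% is −ln(0.55) − 0.431 = 0.598 − 0.431 = 0.167, and 0.0098 is about 6% of that.

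**5. The other endpoints, also by assumption.** For ADR with 35% in both arms, a one-point reading shift (about 5 of 510 patients turned positive) gives a one-sided error of 5.2%. For PPA, the assumed 70% leaves at most 30% of excisions non-significant. If 2% to 5% of those were upgraded in the device arm only (a range with no source), PPA would move by 0.30 × 0.02 = 0.6 to 0.30 × 0.05 = 1.5 points against a 10-point margin.

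**The case against.** The strongest objection is that exposure is not shown. The label and report items in Section 7.2.5 are a sequence number or letter and a location, with no arm. Processing guidance is the same in both arms, and allocation is within colonoscopist. The sentence in Section 7.2.3 may mean only that no formal masking is imposed on routine pathology. All of this stands. A reader might infer that pathologists will know the arm and that APC will be inflated; the documents support neither step. Nor do they contradict themselves here: this is a disclosed design choice.

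The arithmetic is also open to challenge. The documents give no misreading rate, APC mean or dispersion. The higher error rates come from a Poisson model without overdispersion, and overall success requires both co-primary endpoints. The base of 510 applies the data loss, although ITT is defined in the glossary as all randomized subjects. With 600 per arm, five lesions give 1 − Φ(1.96 − 0.00833/0.0379) = 4.1% (Poisson) or 1 − Φ(1.96 − 0.00833/0.0886) = 3.1% (negative binomial), so that choice matters little. The dependence on assumed models stands, and the figures cannot be read as an estimate of bias.

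Finally, Section 13 defers some analysis detail to a SAP whose content is not in the text reviewed. A sensitivity analysis could sit there, but it is unlikely to reverse the rule in Section 7.2.3.

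What the objection does not remove is the rule itself. If the arm never reaches pathology, masking costs little and lets the sponsor report blinded histology. If it does, an avoidable route for bias is closed.

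**Conclusion.** The point holds as a cheap improvement. Section 7.2.3 affirmatively leaves unblinded the readers whose judgement decides APC, ADR and the histological part of PPA, and nothing in the documents offsets this with a masked or central read. Actual exposure is undocumented, and the direction and size of any bias are unknown.

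The calculation supports a limited statement: under no true effect, a handful of one-directional readings would move the APC error visibly under a Poisson model and mildly under the assumed overdispersed one. It does not show that the trial's error rate is inflated. If the planned effect is real, a few lesions would probably not change the conclusion.

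**What to change.** In Section 7.2.3, replace the first blinding sentence with wording such as:

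> Pathologists reading study specimens will be blinded to study arm. Subjects, investigators and all other site personnel remain unblinded. Requisitions, jar labels and clinical notes sent to pathology will state neither the study arm nor EVA-C use. Any known unblinding of a pathologist will be recorded on the protocol deviation CRF and classified under Section 7.2.9.

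Classification should be left to Section 7.2.9 and not fixed in advance as minor, because that section treats events affecting study integrity as major. The histopathology processing guidelines stay as they are.

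**Cost.** A protocol amendment with IRB/IEC approval (Section 12.1), plus site paperwork, training and logging of known unblinding. The readers, specimens and sample size do not change. That the site burden is small is a judgement: requisition content and pathologists' access to procedure reports are not described and may vary by site.

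**Limits.** Masking would apply only to specimens read after the amendment. It does not address the unblinded colonoscopist's choice of what to excise, which sets the PPA denominator, or the location that the colonoscopist reports.

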7.2.4. Subject Compensation

Subjects may be compensated for their participation in the study. The details of compensation will be provided to the subjects in the informed consent form.

7.2.5. Visit Schedule

After confirmation that the ICF has been signed by both the investigator (or designee) and the subject and eligibility has been confirmed, the following assessments will be performed.

- Subjects will be randomized using the randomization system within the EDC system provided by Sponsor.
- If a subject is assigned to the intervention group, the EVA-C System will be turned on prior to scope insertion and will remain on for the duration of the colonoscopy.
- If a subject is assigned to the control group, the EVA-C System will not be used and will remain turned off during the colonoscopy.
- In both the control and intervention groups, the colonoscopy video feed will be recorded from scope-in to scope-out, while the scope is inside the subject. Any

protected health information (PHI) in the colonoscopy video feed will be masked prior to recording or removed after recording, but prior to sending to Sponsor.

Colonoscopy procedure

- High Definition White Light Endoscopy will be used, per standard of care.
- Dye-based or virtual chromoendoscopy may be used for characterizing individual polyps at the colonoscopist's discretion, but may not be used for overall inspection of the colon.
- Bowel preparation will be evaluated after cleaning and will be scored using the Boston Bowel Preparation Scale (BBPS) separately in each of the three regions of the colon: the right colon (including the cecum and ascending colon), the transverse colon (including the hepatic and splenic flexures), and the left colon (including the descending colon, sigmoid colon, and rectum).¹ Subjects with a BBPS score of 0 or 1 in any of the three colonic regions of the colon will be excluded from the Per Protocol analysis.
- In the right, transverse, and left colon, lesions are to be removed, at the colonoscopist's discretion, per standard of care. Notably, in the left colon, only those lesions that appear adenomatous are to be removed, per standard of care.

In the intervention arm only:

System is not intended to change the colonoscopist's management of an identified polyp or lesion.

- The colonoscopist is expected to interrogate any region of interest highlighted by the EVA-C System bounding box.
- In the right, transverse, and left colon, lesions are to be removed, at the colonoscopist's discretion, and irrespective of the EVA-C System bounding box, per standard of care. Notably, in the left colon, only those lesions that appear adenomatous are to be removed, per standard of care.
- For bounding boxes that persist on the screen for at least 2-3 seconds (per colonoscopist's discretion) but do not contain a polyp, the colonoscopist will verbally confirm a 'false alert' to the study personnel.

Polyp resection and pathology processing:

- Endoscopic images of each polyp will be acquired before polyp removal.
- Study personnel will record the polyp size (≤ 5 mm, 6-9 mm, ≥ 10 mm), location (cecum, ascending, hepatic flexure, transverse, splenic flexure, descending, sigmoid, rectum), and morphology (Pedunculated 0-Ip, Sessile 0-Is, Flat 0-IIa, or Depressed 0-IIc in accordance with Paris classification²), as reported by the colonoscopist.

 Study personnel will record the time-of-day at the moment the colonoscopist says 'snare closed' (or as the snare is closed) and each polyp will be assigned a number or letter in the sequential order in which it is removed (eg. 1, 2, 3,... or A, B, C, ...) per standard of care.

- If the polyp is not able to be retrieved, the study personnel will note 'not retrieved' in the source documentation.
- Each polyp will be placed into an individually labeled specimen jar with only one polyp per specimen jar. If a polyp trap is used on the endoscope, the polyp trap needs to be advanced/rotated for each new resected polyp.
- The specimen jar will be labeled with the sequential number or letter correlating to the order in which the polyp was removed (eg. 1, 2, 3,... or A, B, C,...) per standard practice.
- The pathology report will note each sequential polyp number or letter and location per standard practice.

Pathology processing guidelines:

- Histopathology will be performed per standard of care with the following recommended guidelines. As assessed by pathologists:
 - For polyp sizes of 1 cm and greater:

Recommend allowing at least 24 hours in formalin for fixation prior to sectioning. Serial section (through stalk, if present) into a maximum of 3 mm blocks. For each block, recommend at least 2 sections will be acquired.

• For polyp sizes greater than 6mm and less than 1cm:

Bisect or serial section (through stalk, if present) into a maximum of 3 mm blocks. For each block, recommend at least two sections will be acquired.

• For polyp sizes between 3mm and 6mm, inclusive:

Recommend at least two slides with 8 ribbon sections per slide. For 'no significant abnormality' findings, at least 3 serial sequential deeper levels will be performed. Exhaust the block on Pathologist's discretion.

• For polyp sizes less than 3mm:

Recommend to ribbon section block entirely ('exhaust the block' – at least 3 slides)

 Histopathology sections shall be stained and imaged as per standard of care.

Review of Adverse Event, Protocol Deviation, and Device Deficiencies will be completed from time of consent to study exit.

